9.3 Endpoints

9.3.1 Primary

- DLTs, classified and graded according to the NCI CTCAE, version 5.0.
- Frequency of treatment-emergent adverse events (TEAEs), and serious adverse events (SAEs) related to APR-246 in combination with venetoclax and/or azacitidine during the trial.
- The RP2D of APR-246 (the dose at which <2 out of 6 patients experience dose-limiting toxicity during the safety assessment period).

9.3.2 Secondary

1. CR rate, defined as the proportion of patients who achieve CR.
2. CR + CRi rate, defined as the proportion of patients who achieve CR or CRi.
3. CR + CRh rate, defined as the proportion of patients who achieve CR or CRh.
4. ORR, defined as the proportion of patients achieving CR, CRi, CRp, PR and MLFS by the IWG 2003 AML criteria ([APPENDIX I](#)). The CRh rate will also be determined and is defined as bone marrow blasts $<5\%$, ANC $>0.5 \times 10^9/L$ and platelets $>50 \times 10^9/L$.
5. OS, measured from the date of initiating study treatment to the date of death. Patients who have not died by the analysis data cut-off date will be censored at their last date of contact.

6. Rate of RBC and/or platelet TI for at least 56 days
7. PFS, defined from the date of initiating study treatment to the date of disease progression per IWG 2003 AML criteria ([APPENDIX I](#)) or death as a result of any cause.
8. Proportion of patients who transition to HSCT.
9. Pharmacokinetic parameters: C_{max} , AUC, V_d and CL of APR-246 and T_{max} , C_{max} and AUC of venetoclax.

9.3.3 Exploratory

- Exploratory molecular analyses may include, but are not limited to: *TP53* VAF by NGS, p53 IHC, mutations in other genes by NGS, RNA expression.

9.4 Safety

Safety data will be summarized for the safety population. These data will include AEs, ECGs and laboratory parameters. AE terms will be coded using the Medical Dictionary for Drug Regulatory Activities (MedDRA)[®], version 22 or higher. AEs will be summarized by System Organ Class (SOC), preferred term, severity, and relationship to treatment. Serious adverse events, deaths, and AEs leading to dose modifications including early discontinuation of study treatment will be summarized. Laboratory parameters will be summarized by maximum NCI CTCAE version 5.0 severity grade and also by change from pre-treatment to scheduled time points using descriptive statistics. Laboratory parameter listings will include the normal ranges for each parameter. Each value will be classified as falling above, below, or within the normal range.

Only AEs related to study screening procedures are to be collected prior to the initiation of study treatment. Data summaries will include only treatment-emergent adverse events (TEAEs), defined as events occurring at the start of infusion on Day 1, Cycle 1 up to and including 30 days after last dose.

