- q. Please consult Section [8.4](#) for PK collection schedule.
- r. Patients discontinuing treatment should complete their end of treatment visit within approximately 28 days of their last dose of APR-246. Physical exam, vital signs, clinical toxicity assessment, hematology, serum chemistry and bone marrow aspirate and biopsy with NGS analysis should be performed, if feasible.
- s. Long-term follow up can be done remotely (e.g. via telephone, via local practitioner or via review of medical records). Assuming there is no withdrawal of consent, patients who stop study treatment for any reason (e.g. toxicity, transition to SCT, PD) will continue long-term follow-up (see Section [7.4](#)). If a patient is removed from the study due to unacceptable AEs, the event(s) will be followed until resolution or stabilization of the AE. Off-treatment data on overall survival will be updated every month (i.e. every 28 days \pm 3 days) or until death or withdrawal of consent for study participation, whichever occurs first. If a patient is removed from the study due to unacceptable adverse events (AEs), the event(s) will be followed until resolution or stabilization of the adverse event. Patients who respond and discontinue study treatment for reasons other than PD should have response assessments and survival should be collected every month until relapse, death or withdrawal of consent for study participation, whichever occurs first. After relapse, data for

survival should be collected every month (i.e. every 28 days ± 3 days) until death or withdrawal of consent for study participation, whichever occurs first.

- t. AE description, grade and start date and resolution date should be documented.

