7.3 End of Treatment Visit

This visit should take place within 28 days of the last dose of study treatment, if treatment is stopped early for any reasons.

- Physical examination
- Weight
- Vital signs
- Disease assessment
- Bone marrow aspirate for exploratory objectives. If no aspirate is available, then peripheral blood is acceptable
- ECOG performance status ([APPENDIX III](#))
- Hematology, including complete blood count with white blood cell differential
- Serum chemistry, including sodium, potassium, chloride, magnesium, CO₂, BUN, creatinine, glucose, calcium, albumin, total protein, total bilirubin, AST, ALT, alkaline phosphatase
- Clinical toxicity assessment up to 30 days after the last dose

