8.1.2 Reporting of Adverse Events

8.1.2.1 Adverse Events

An AE is any untoward medical occurrence in a patient or clinical investigation subject administered a pharmaceutical product that does not necessarily have a causal relationship with the treatment. An AE can be any unfavorable and unintended sign (including a laboratory finding), symptom or disease temporally associated with the use of a medicinal (investigational) product, whether or not related to the medicinal (investigational) product.

The treatment-emergent AE reporting period starts at study treatment initiation. All treatment-emergent AEs will be collected for up to 30 days after the last dose of study treatment. At each evaluation, patients should be interviewed in a non-directed manner to elicit potential adverse reactions from the patient. The occurrence of an AE will be based on changes in the patient's physical examination, laboratory results, and/or signs and symptoms.

On Cycle 1, Day 1, any events observed from the time of signing informed consent but prior to initial study drug administration will be recorded as a serious or non-serious adverse event, if considered by the Investigator to be causally related to a study-required procedure or activity that was conducted prior to Cycle 1, Day 1 (i.e., screening period). Events observed from the time of signing informed consent, but prior to initial study drug administration that are not considered to be causally related to a study-required procedure or activity should be recorded on the medical history CRF page.

All AEs (except Grade 1 and 2 laboratory abnormalities that do not require an intervention), regardless of causal relationship, are to be recorded in the CRF and source documentation. The Investigator must determine the intensity of any AEs according to the NCI Common Terminology Criteria for Adverse Events (CTCAE) version 5.0 and their causal relationship. Those AEs not covered by these criteria will be graded as follows:

1. Mild: Discomfort noticed, but no disruption of normal daily activity. Prescription drug not ordinarily needed for relief of symptom but may be given because of personality of patient.
2. Moderate: Discomfort sufficient to reduce or affect normal daily activity. Patient is able to continue in study; treatment for symptom may be needed.

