8.1.2.6 Reporting of Serious Adverse Events

AEs classified as serious require expeditious handling and reporting to Sponsor's monitoring CRO to comply with regulatory requirements.

For any serious adverse event (SAE) that occurs while a patient is on-study; within 30 days of the last study treatment administration, regardless of any opinion as to the relationship of the SAE to the study treatment; or if any SAE that the Investigator feels is related to the study treatment occurs later than 30 days after the last study treatment administration, the Sponsor's monitoring CRO must be notified immediately (within 24 hours of becoming aware of the event) by electronic data capture (EDC) system, email, fax or telephone. Notification by email is preferred. The primary mechanism for reporting an SAE to the sponsor will be the electronic data collection tool. An SAE eCRF should be completed in the electronic data capture (EDC) system within 24 hours of site becoming aware of the event. EDC Alerts will be sent to Safety desk for all SAEs.

If the EDC system is inaccessible/unavailable, then the site will use the paper SAE form in order to report the SAE within 24 hours. Emailing the paper SAE forms is the preferred method of notification.

SAEs will be reported to: Email: [REDACTED]

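### The Section 9.4 limit on safety summaries conflicts with the primary endpoint for late related SAEs, and the end-of-treatment visit has two different anchors

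*Combined protocol and SAP*

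**What the plan says.** **What is summarised.** Section 9.4 states "Data summaries will include only treatment-emergent adverse events (TEAEs" and ends that class at "up to and including 30 days after last dose". The same section also says "Serious adverse events, deaths, and AEs leading to dose modifications including early discontinuation of study treatment will be summarized", with no time limit.

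**What the endpoint counts.** One primary endpoint in Section 9.3.1 (repeated in the synopsis) is the frequency of TEAEs and of "serious adverse events (SAEs) related to APR-246 in combination with venetoclax and/or azacitidine during the trial". Section 4.2 ends the study at the last patient's last visit, and Section 7.4 follows patients until death or withdrawal of consent.

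**What is collected.** Section 8.1.2.1 says "All treatment-emergent AEs will be collected for up to 30 days after the last dose of study treatment". For SAEs, Section 8.1.2.6 goes further: the CRO must also be told within 24 hours of "any SAE that the Investigator feels is related to the study treatment occurs later than 30 days after the last study treatment administration". The SAE eCRF is the primary route.

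**When the last on-site visit falls.** Footnote r to the study calendar (Table 8) says "Patients discontinuing treatment should complete their end of treatment visit within approximately 28 days of their last dose of APR-246". Section 7.3 says "This visit should take place within 28 days of the last dose of study treatment".

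**The concern.** Safety is the primary objective, and these event counts are a primary endpoint. Two features of the text could make the reported counts differ from what the endpoint describes.

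First, a related SAE that starts more than 30 days after the last dose fits the endpoint as worded and should be in the database. The restriction in 9.4, taken at its word, then keeps it out of the tables. Overall survival would show a late death but not its relatedness, and a non-fatal late related SAE has no other place in the planned analyses.

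Second, the end-of-treatment visit carries the physical examination, vital signs, hematology, chemistry and toxicity assessment. If sites follow footnote r in a venetoclax cohort, that visit is due much earlier relative to the end of the 30-day window than if they follow 7.3. Follow-up after the visit may be remote. Its text names survival, response in responders who stopped for reasons other than progression, and resolution of AEs that led to removal; it does not name a question about new AEs.

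**Working it through.** **Part 1: the passages side by side (no arithmetic applies)**

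| Provision | Late related SAE (onset more than 30 days after last dose) |
|---|---|
| 9.3.1, primary endpoint | Counted: the period is the trial, with no 30-day limit |
| 8.1.2.6, reporting | Captured: must be reported, no upper time limit |
| 9.4, sentence on SAEs and deaths | Summarised: no window given |
| 9.4, TEAE-only sentence | Not summarised: window closes at 30 days |

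Three provisions include the event and one excludes it. The excluding sentence is the one that says what the summaries may contain, so a programmer working from 9.4 could defend either output.

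**Part 2: day arithmetic**

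Inputs, numbered within the last cycle:
- last scheduled APR-246 dose: Day 4 (6.1.1; Table 8 footnote g);
- last venetoclax dose in a full cycle: Day 28 (daily dosing in 6.1.2, 28-day diary in Appendix VI); 4.1 also allows 14 to 21 days in later cycles for some responders;
- last azacitidine dose: Day 7 (6.1.3), or Day 10 if the permitted 3-day interruption is used;
- visit allowance: 28 days (footnote r and 7.3);
- AE window: 30 days after the last dose (8.1.2.1, 9.4).

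Let A be the day of the dose that anchors the visit and L the day of the last dose of any study drug. The visit deadline is A + 28, the window closes on L + 30, and the deadline gap is (L + 30) − (A + 28). Under footnote r, A is the last APR-246 day. Under 7.3, A = L, so the gap is 30 − 28 = 2 in every case.

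| Last cycle | Footnote r deadline | 7.3 deadline | Window closes | Gap, r | Gap, 7.3 |
|---|---|---|---|---|---|
| Venetoclax to Day 28 | 4 + 28 = 32 | 28 + 28 = 56 | 28 + 30 = 58 | 26 | 2 |
| Venetoclax to Day 21 | 32 | 49 | 51 | 19 | 2 |
| Venetoclax to Day 14 | 32 | 42 | 44 | 12 | 2 |
| Cohort 5, azacitidine to Day 7 | 32 | 35 | 37 | 5 | 2 |
| Cohort 5, azacitidine to Day 10 | 32 | 38 | 40 | 8 | 2 |
| All drugs stop on Day 4 | 32 | 32 | 34 | 2 | 2 |

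After a full venetoclax cycle, 26 of the 30 post-dose days (26/30 = 87%) fall after the footnote-r deadline.

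**Limits of these figures.** They are gaps at the visit deadline, not maxima. If the last APR-246 dose was on Day 1 and venetoclax ran to Day 28, the footnote-r gap is 58 − 29 = 29 days. Both rules set only a latest date, and footnote r makes it approximate. Under 7.3 a visit on Day 28 complies and leaves 58 − 28 = 30 days. So 2 days is the smallest gap that 7.3 permits, not one it guarantees, and a change of anchor alone does not secure observation to the end of the window.

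**The case against.** The strongest reply is that nothing is lost. Section 9.4 itself promises a summary of SAEs and deaths without a window, and the TEAE-only sentence directly follows one about events before treatment, so it can be read as defining the routine AE tables. Late related SAEs reach the eCRF, the medical monitor reviews all SAEs as reported, and data review meetings discuss all accumulated safety data (8.1.2.7). The DLT and RP2D endpoints rest on the lead-in DLT assessment and are unaffected. AE collection to 30 days is required by 8.1.2.1, by 7.3 and by the calendar's toxicity row, and 8.1.2.1 follows related events to resolution or stabilisation, subject to stated exceptions.

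Most of this stands, and it rules out several stronger readings that a reader might infer:

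- *The plan plainly drops every late related SAE.* It does not. Section 9.4 conflicts with itself; total exclusion follows only from the literal reading of one sentence, and it is exclusion by definition, not an estimate of events missed.
- *AE collection ends at the visit, or rests on spontaneous reports.* The text still requires collection to 30 days. It does not tie that collection to a scheduled contact at the end of the window.
- *Patients who stop APR-246 but continue another study drug go unobserved.* Footnote r addresses patients discontinuing treatment, and anyone still treated keeps the calendar's cycle visits.
- *No blood tests follow the visit.* Table 8 is damaged in the available text, and its hematology row may carry a mark under long-term follow-up, so this cannot be asserted.

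The reply does not remove either contradiction. Review by the medical monitor does not put an event into the table that reports the primary endpoint, and two anchors for one visit will be applied differently by different sites.

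**Conclusion.** Both inconsistencies are real and should be corrected. The rules for the primary safety summary disagree on whether a related SAE after 30 days counts; if the restrictive sentence governs, such events are captured and then left out. The number affected is unknown, because the documents give no rate.

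The end-of-treatment visit has two deadlines: 24 days apart after a full venetoclax cycle (56 − 32) and 3 days apart in Cohort 5 (35 − 32). This bears on scheduled examinations and laboratory tests late in the window, not on whether AEs must be recorded. The figures assume dosing as scheduled and a visit on its last permitted day. If either defect has an effect, it is towards under-counting; neither shows that an under-count will occur.

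**What to change.** 1. **Section 9.4.** Keep the 30-day TEAE tables and state that the TEAE restriction applies to them. Add a summary of treatment-related SAEs, including fatal ones, regardless of onset, so that the result matches 9.3.1 and 8.1.2.6.
2. **Table 8, footnote r.** Reconcile with 7.3 by timing the end-of-treatment visit from the last dose of any study drug.
3. **Section 7.4 and footnote s.** Because a visit within 28 days can fall well before the window closes, add a question about AEs and SAEs at the first monthly follow-up contact made 30 or more days after the last dose.

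The cost is wording changes, one extra table, one question on a contact already planned every 28 days, and slightly higher reported event counts. A related-SAE question at every later monthly contact would be a further option, but it is a matter of preference and not needed to resolve the conflict.

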9.5 Efficacy

CR will be summarized for all enrolled patients as the proportion of patients (%) with CR. In addition to presenting the CR rate, its associated exact 95% CI for each treatment arm will also be presented. CR rate will not be formally compared between treatment arms.

DoR will be defined as the time from the date when criteria for response are met to the date of PD or death due to any cause, whichever occurs first. Patients that are alive without relapse or progression will have their DOR censored at the date of the last clinical assessment. The duration of CR will be summarized in each treatment arm by providing DOCR and DOR, using Kaplan-Meier methodology. DoR endpoints will not be formally compared between treatment arms.

Overall response will be summarized in number (%) of patients in each category of responses and ORR will be analyzed by using the similar method as CR rate.

Survival data will be collected at treatment and follow-up periods. Patients will be followed until death, or withdrawal of consent for study participation. OS is defined as the number of days from the date of enrollment to the date of death. Kaplan-Meier methodology will be utilized.

PFS will be defined as the time from the date of enrollment to disease progression or death from AML whichever occurs first. If neither event occurs, PFS will be censored at the date of the last assessment. Kaplan-Meier methodology will be utilized.

Transition rate to SCT will be analyzed using the similar methods as CR.

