	
DRT consisting of the Medical Monitor, Site Principal Investigators, and other clinical research personnel that the Sponsor may deem appropriate, will hold DRM on an interim basis at a frequency dependent on study accrual. At these meetings, the DRT will review AEs and DLT and make recommendations regarding the RP2D. In the expansion portion of the study, the DRT will evaluate safety and tolerability after 5 patients have completed 1 cycle of treatment in each cohort. All accumulated safety data will be discussed during DRMs.
 
Determination of Sample Size
 
This trial assumes a sample size of 12 – 36 patients (6 – 18 patients for each cohort) in the safety lead-in portion of the study and approximately 70 patients in the expansion portion of the study.
 
Analysis Populations
 
Safety population: Patients will be evaluable for safety if they receive at least one dose of APR-246 with venetoclax and/or azacitidine. The safety population will be used to summarize exposure and safety parameters.
 
DLT-evaluable population: All patients who either experienced a DLT during first the 4 weeks (Cycle 1) of the study treatment or received $\geq 80\%$ of scheduled Cycle 1 dose of APR-246 in combination with venetoclax and/or azacitidine and did not experience a DLT. Any individual patient who is not evaluable for DLT will be replaced by a new patient through additional patient enrollment.
 
Efficacy evaluable (EE) population: All patients who complete at least one treatment cycle of APR-246 in combination with venetoclax and/or azacitidine and who have at least one post-treatment clinical response assessment. Patients who fail to complete one treatment cycle will also be considered EE if they show clear evidence of clinically significant disease progression. The EE population will be the secondary analysis population for efficacy.
 
Pharmacokinetics (PK) population: Patients will be evaluable for pharmacokinetics if at least one post-dose sample for PK evaluation has been obtained.
 
Efficacy Analyses
 
CR will be summarized for all enrolled patients as the proportion (%) of patients with CR. In addition to presenting the CR rate, its associated exact 95% confidence intervals (CI) for each treatment arm will also be presented. CR rate will not be formally compared between treatment arms.
 
CR + CR_h rate will be summarized as the proportion of patients who achieve CR or CR_h. CR_h is defined as bone marrow blasts $< 5\%$, ANC $> 0.5 \times 10^9/L$ and platelets $> 50 \times 10^9/L$. CR + CR_i rate will be summarized as the proportion of patients who achieve CR or CR_i. The rate of TI will be summarized as the proportion of patients with RBC and/or platelet TI for at least 56 days.
 
Duration of response (DoR) is defined as the time from the date when criteria for response are met to the date of relapse or progressive disease (PD) or death due to

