--	--

	
any cause, whichever occurs first. Patients alive with no progressive disease will have their DOR censored at the date of the last clinical assessment. The duration of CR will be summarized in each treatment arm by providing duration of complete response (DOCR) and duration of overall response (DOR), using Kaplan-Meier methodology. DoR endpoints will not be formally compared between treatment arms.
 
Overall response will be summarized in number (%) of patients in each category of responses and ORR will be analyzed by using the similar method as CR rate.
 
Survival data are collected at treatment and follow-up periods. Patients will be followed until death or withdrawal of consent for study participation. Overall survival (OS) is defined as the number of days from the first day of treatment to the date of death. Kaplan-Meier methodology will be utilized.
 
Progression-free survival (PFS) is defined as the time from the first day of treatment to disease progression or death from AML, whichever occurs first. If neither event occurs, PFS will be censored at the date of the last clinical assessment. Kaplan-Meier methodology will be utilized.
 
Safety Analyses
 
Safety data including AEs, vital signs, laboratory data, electrocardiogram (ECG), physical exam will be tabulated for the safety population. AEs will be tabulated by System Organ Class (SOC), preferred term, severity, and relationship to treatments. The tabulation of laboratory parameters will include the normal ranges for each parameter. Each value will be classified as falling above, below, or within the normal range. Laboratory parameters will also be tabulated by maximum NCI CTCAE v5.0 severity grade.
 
Pharmacokinetic Analysis
 
PK sampling for APR-246 are performed in Cycle 1, on Days 1, 2 and 4, and on Day 4 of every subsequent cycle.
 
PK sampling for venetoclax is performed on Days 1, 2, 22 and 23 of Cycle 1 and on Day 4 of Cycles 2 – 5.
 
Non-compartmental or population pharmacokinetic methods will be used to derive APR-246 and venetoclax PK parameters (C_{max}, T_{max}, AUC, V_d and CL).
 
The pharmacokinetics of APR-246 and venetoclax will be summarized using descriptive statistics (mean, standard deviation, CV% mean, geometric mean, CV% geometric mean) and compared with historical control data.
 
APR-246 AUC and C_{max} will then be tested for association with signs of efficacy and safety. If an observable trend exists, a PK/PD model will be developed to evaluate the exposure-response relationship between APR-246 plasma exposure and outcome measures in the presence of venetoclax. Demographic and clinical data (ethnicity, current age, body weight, sex, disease status, etc.) will be utilized to assess interpatient variability in the PK and PK/PD relationships.

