8.2.2 Duration of Response

DoR will be measured from the time of initial response to disease relapse/progression or death.

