8.2.5 Stem Cell Transplant

Patients may go on to receive SCT and this is likely to be a reflection of a positive outcome to treatment. The primary approach will be to use a treatment policy strategy (ICH E9 (R1) addendum) where patients who receive SCT will continue to be followed for OS and relapse from any response with their date of death/relapse used in the analysis. If for any reason a patient receives SCT prior to a documented CR they will not be counted as a response. Sensitivity analyses may be performed as counting post-SCT CR/PR as a response.

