
APPENDIX I – Response Criteria Based on Modified Recommendations of the International Working Group for Diagnosis, Standardization of Response Criteria, Treatment Outcomes, and Reporting Standards in Acute Myeloid Leukemia⁵⁹

Response Criterion	Neutrophils, ×10 ⁹ /L	Platelets, ×10 ⁹ /L	Bone Marrow Aspirate Blasts (%) (by biopsy acceptable if aspirate not available)
CR	>1.0	>100	<5
CRI	ANC ≥1,000 OR platelets ≥100,000		<5
MLFS	NA	NA	<5
PR	>1.0	>100	>50% decrease from baseline to level of 5-25%
SD (for patients without a prior best response of CR, CRI, MLFS, or PR)	Absence of CR, CRI, PR, MLFS; and criteria for PD not met		
Hematologic relapse (for patients with a prior best response of CR, CRI, MLFS)	Bone marrow blasts ≥5%, or reappearance of blasts in the blood, on two consecutive assessments separated by ≥28 days. Development of new extramedullary disease.		
PD (for patients with a prior best response of SD or PR)	
Evidence for an increase in bone marrow blast percentage and/or increase of absolute blast counts in the blood, on two consecutive assessments at least 28 days apart:
 
>50% increase in marrow blasts over baseline (a minimum 15% point increase is required in cases with <30% blasts at baseline; or persistent marrow blast percentage of >70% over at least 3 months; without at least a 100% improvement in ANC to an absolute level ($>0.5 \times 10^9/L$ [500/mL], and/or platelet count to $>50 \times 10^9/L$ [50,000/mL] non-transfused); or
 
>50% increase in peripheral blasts (WBC × % blasts) to $>25 \times 10^9/L$ ($>25,000/mL$) (in the absence of differentiation syndrome); or
 
New extramedullary disease
		

Additional Responses to be Assessed in Addition to Above Responses
 
These responses in addition to other responses and do not have specific hematologic criteria.
			
Cytogenetic CR	Normal karyotype in a patient with abnormal cytogenetics at baseline.		

TP53 Molecular CR	TP53 mutation not detected by NGS based on local testing in a patient with detectable TP53 VAF by NGS at baseline.

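### Section 9.5 leaves relapse out of the duration-of-response event, which contradicts its own censoring sentence and three other places in the protocol

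*Combined protocol and SAP*

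**What the plan says.** The combined protocol and SAP defines DoR in several places, and they do not agree.

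- **Section 9.5, event:** DoR runs "from the date when criteria for response are met to the date of PD or death due to any cause". Relapse is not named.
- **Section 9.5, censoring (next sentence):** "Patients that are alive without relapse or progression will have their DOR censored at the date of the last clinical assessment".
- **Section 8.2.2:** "DoR will be measured from the time of initial response to disease relapse/progression or death".
- **Synopsis, Efficacy Analyses, event:** the interval runs "to the date of relapse or progressive disease (PD) or death due to" any cause.
- **Synopsis, censoring:** "Patients alive with no progressive disease will have their DOR censored at the date of the last clinical assessment". Relapse is not named here.
- **Section 8.2.5, patients transplanted on study:** they are followed for OS and for "relapse from any response with their date of death/relapse used in the analysis".

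Appendix I separates the two disease events by prior best response. One row is headed "PD (for patients with a prior best response of SD or PR"); the other is headed "Hematologic relapse (for patients with a prior best response of CR, CRI, MLFS").

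ORR in Section 9.3.2 counts CR, CRi, CRp, PR and MLFS. Section 9.5 summarises duration of complete response (DOCR) and duration of overall response by Kaplan-Meier, without formal comparison between arms.

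**The concern.** Of the five response categories in ORR, the Appendix I definition of PD reaches only PR. CR, CRi and MLFS fall under hematologic relapse, and CRp has no row in Appendix I. For DOCR, which concerns CR patients only, the disease event named in the Section 9.5 event sentence cannot occur, so that sentence leaves death as the only event.

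DOCR and DoR are the plan's durability summaries. If relapse were not counted, a patient could be shown as still in response after the leukemia had returned, and the Kaplan-Meier median would be too long. If the analyst instead followed Section 8.2.2, the same data would give a shorter median. No clause says which section prevails.

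PFS, a listed secondary endpoint, has a related gap. None of its definitions (synopsis endpoints, synopsis statistics, Sections 8.3, 9.3.2 and 9.5) names relapse, and Section 9.3.2 ties progression explicitly to Appendix I.

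**Working it through.** **Step 1. Apply each rule to one patient.** Take a patient who reached CR, has since had hematologic relapse under Appendix I, and is alive at data cut-off.

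| Rule | Event at relapse? | Censored? |
|---|---|---|
| Section 9.5, event and censoring sentences | No: relapse is not named, and PD does not apply after CR | No: the patient is not free of relapse |
| Section 8.2.2 | Yes | No rule given |
| Synopsis, event and censoring sentences | Yes | Also yes if PD has its Appendix I meaning: alive with no PD |
| Section 8.2.5 (if transplanted) | Yes: relapse date used | No rule given |

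Section 9.5 gives this patient no status. The synopsis, read strictly, gives two. Section 8.2.2 gives one.

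**Step 2. Could PD simply stand for relapse?** Not without moving the event date, because the Appendix I criteria differ. Relapse needs marrow blasts of at least 5%, or blasts back in the blood, on two assessments at least 28 days apart, or new extramedullary disease. The marrow route to PD needs a rise of more than 50% over baseline. With 30% blasts at baseline, that means above 30 × 1.5 = 45%, against 5% for relapse.

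**Step 3. Size.** The plan states no DoR figure to reproduce, so this is an illustration on assumed inputs:

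- *m*, true median time from response to relapse or death: 6 months (assumed), or 11.3 months (the all-patient venetoclax plus HMA median DoR in Section 2.3, which is not a *TP53*-mutant figure).
- *q*, share of first events that are relapse: 0.6 or 0.8 (assumed). The remainder are deaths in response, which are events under every wording.
- *s*, median survival after relapse: 2, 4 or 6 months (assumed).
- All times exponential, with λ = ln 2 / *m* and μ = ln 2 / *s*.

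If relapse is ignored and only death ends the response, the probability of still being counted as in response at time *t* is

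S(t) = exp(−λt) + qλ [exp(−μt) − exp(−λt)] / (λ − μ),

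with second term qλt·exp(−λt) when λ = μ. The apparent median solves S(t) = 0.5.

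Example with *m* = 6, *q* = 0.6, *s* = 2: λ = 0.1155 and μ = 0.3466. At t = 7.9 the first term is 0.401. The second is 0.0693 × (0.0647 − 0.4015) / (−0.2310) = 0.101. The sum is 0.50.

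| True median *m* | *q* | *s* = 2 | *s* = 4 | *s* = 6 |
|---|---|---|---|---|
| 6 | 0.6 | 7.9 | 9.6 | 10.9 |
| 6 | 0.8 | 8.6 | 10.8 | 12.7 |
| 11.3 | 0.6 | 13.2 | 15.2 | 16.9 |
| 11.3 | 0.8 | 13.8 | 16.4 | 18.7 |

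The overstatement runs from 7.9 − 6 = 1.9 months to 18.7 − 11.3 = 7.4 months. In the limiting case where every first event is a relapse and *s* is 3 to 6 months, the medians are 10.6 to 14.5 instead of 6, and 16.0 to 20.5 instead of 11.3. That is an upper case, because it allows no deaths in remission.

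**The case against.** A reader might infer from the Section 9.5 event sentence that, under this plan, relapse from CR, CRi or MLFS does not end a response, and that DOCR is simply time from CR to death. The documents do not support that. The very next sentence of Section 9.5 withholds censoring from relapsed patients, and Section 8.2.2, the synopsis event sentence and Section 8.2.5 all count relapse. The likely intent is clear, and only one event clause departs from it. Nor does time from CR to death follow from Section 9.5 itself, which leaves the living relapsed patient undefined.

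It can also be said that PD is used loosely elsewhere. The follow-up text (synopsis, Table 8 footnotes, Section 7.4) speaks of responders who stop treatment for reasons other than PD and are then assessed until relapse. On the strict Appendix I meaning, a CR patient could never stop for PD. This makes the literal reading less likely in practice. However, Section 5.6.1 distinguishes relapsed from progressive disease, so loose usage does not settle what Section 9.5 means.

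Finally, the stakes are limited. DoR is not in the endpoint lists of Section 9.3, it is not formally compared, and no decision rule depends on it. All of this stands. It bounds the size of the problem, but it does not make the event sentence consistent with the rest of the document.

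**Conclusion.** The inconsistency is real. The Section 9.5 event sentence omits relapse, and Appendix I makes the omission matter because PD cannot apply after CR, CRi or MLFS. The event sentence conflicts with its own censoring sentence, Section 8.2.2, the synopsis event sentence and Section 8.2.5. The synopsis censoring sentence has the opposite slip, naming progressive disease only. The supportable conclusion is that the rule is contradictory, and undefined for a living relapsed patient under Section 9.5 alone. It is not that the plan as a whole carries responses past relapse.

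If relapse were left uncounted, the median would be too long by about 1.9 to 7.4 months over the range examined. This rests on exponential times and on assumed values for the relapse share, for survival after relapse and for the 6-month median; the 11.3-month median is not specific to *TP53*-mutant disease. No alpha, power or sample size changes. The correction should be made before analysis, so that the reported duration does not depend on which section the programmer followed.

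**What to change.** 1. **Section 9.5, DoR and DOCR event.** State it as the first of: hematologic relapse per Appendix I (prior CR, CRi, CRp or MLFS), PD per Appendix I (prior PR), or death from any cause. CRp must be placed explicitly because it counts in ORR but has no Appendix I row.
2. **Censoring.** In both Section 9.5 and the synopsis, censor only patients alive without relapse or progression, at the last clinical assessment.
3. **PFS.** In the synopsis (endpoints and statistics) and Sections 8.3, 9.3.2 and 9.5, state the event as hematologic relapse (prior CR, CRi, CRp or MLFS), PD (all other patients, including SD and PR) or death from any cause. The DoR list must not be copied across unchanged: its PD term covers PR only and would remove the progression event for SD patients. The synopsis statistics text and Section 9.5 currently limit the PFS death event to death from AML, whereas Sections 8.3 and 9.3.2 count any death, so the same edit should settle that.

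The cost is a few sentences across the synopsis and the sections named. No new assessments are needed, because responders are already assessed for relapse on treatment and in follow-up. Durations reported under the corrected rule will be shorter than if relapse had gone uncounted.
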